10.3.2 Treatment Visits

During the double-blind treatment period (Weeks 1 to 48), subjects will return to study site according to the schedule presented in [Table 1](#).

Subjects will self-administer 40 mg of M923 or EU RPP every 2 weeks (Q2W) starting at Week 1 of the study.

Prior to administration of IP, the following assessments will be done at all visits unless otherwise indicated:

- Patient-reported questionnaires: DLQI and EQ-5D-5L (to be completed prior to any other assessments being done [Weeks 16, 25, and 37])
- Review of concomitant medications/non-drug therapies
- AE monitoring
- sPGA, PASI, BSA evaluation

- Brief physical examination (Weeks 4, 8, 17, 19, 25, 27, 37, and 39; complete physical examination at Week 16)
- Vital signs (body temperature, pulse rate, blood pressure, respiratory rate, and measure body weight)
- 12-lead ECG (Weeks 16, 25, and 37)
- PK and immunogenicity (Weeks 8, 16, 17, 21, 25, 29, 37, and 41)
- Clinical laboratory assessments (hematology and serum chemistry; all visits, except Weeks 12, 27, 33, 39, and 45)
- Urinalysis (Weeks 4, 8, 16, 17, 19, 21, 25, and 37)
- Urine pregnancy test (female subjects of childbearing potential only; all visits, except Weeks 1, 19, 27, 39 and 45)
- Study drug dispensing
- Study drug injection in clinic by subject or caregiver (as directed by study site staff)(Weeks 1, 17, 19, 21, 25, 27, 37, and 39)
 - Post-injection monitoring for 2 hours post-injection (clinic only; Weeks 1, 17, 25, and 37)
 - Post-injection observation for 30 minutes post-injection (clinic only; Weeks 19, 21, 27, and 39)
- Study drug injection at home, but after assessments completed at clinic visit (Weeks 29, 33, 41, and 45)
- Study drug injection at home in-between clinic visits (Weeks 3, 5, 7, 9, 11, 13, 15, 23, 31, 35, 43, and 47)
- Injection site evaluation either by clinical staff (at clinic visits) or by the subject or caregiver (administration at home) per [Section 12.10](#)

At Week 16, subjects in Arm B will be randomly assigned again to a new treatment group:

- Arm B1: Continues EU RPP from Weeks 17 through 48 (last dose at Week 47; n = up to 129 subjects)
- Arm B2: Transition to M923 at Week 17; then to EU RPP at Week 25; and to M923 at Week 37 (last dose at Week 47; n = up to 129 subjects)

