6.5 Extent of Exposure

Exposure to study medication will be provided. Exposure will be calculated overall as well as for exposure up to Week 16 and for week 16 onwards. The number of days on study medication (duration of exposure = date of last dose of IP in given time period minus date of first dose of IP +1; if either date is missing, the duration is unknown) will be summarized for each treatment group, presenting mean, median, standard deviation, and range.

Exposure will also be calculated and summarized in terms of patient treatment years.

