8. SAFETY EVALUATION

All safety assessments will be summarized and evaluated utilizing the safety analysis set, including AEs, physical examinations, clinical laboratory evaluations, vital signs, 12-lead ECG results and injection site reactions and will be listed and summarized with number and proportion of subjects or descriptive statistics, as appropriate, by treatment arm and analysis period (Arm A and B up to Week 16; Arm A, B1 and B2 after Week 16). Subjects who withdraw from the study prematurely will have their Early withdrawal visit summarized as an individual visit. No formal hypothesis testing of safety data is planned.

Further details are provided in the following sub-sections.

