The number and percentage of subjects with any AE, any related AE, any severe AE, any related severe AE, any SAE, and any related SAE, as well as the total number of events for each category, will be summarized by treatment group. The number of deaths due to an AE, hospitalization due to an AE and study discontinuation due to an AE will be summarized by treatment arm and analysis period (Arm A and B up to Week 16; Arm A, B1 and B2 after Week 16).

The number and percentage of subjects with an AE, as well as the total number of AEs, will be summarized for each treatment arm and analysis period (Arm A and B up to Week 16; Arm A and B2 after Week 16). This tabulation will be repeated by relationship and severity.

AEs that occurred before first dose of study drug will be listed separately. Any adverse events reported more than 30 days after a subject has completed or withdrawn early from the study, will not be summarized but will be listed.

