10. EVALUATION OF IMMUNOGENICITY

The immunogenicity analysis will be performed on the safety population.

Immunogenicity data (overall ADA results and titers, and neutralizing ADA results and isotype of ADA where applicable, and time to seroconversion) will be listed by analysis tier; specifically:

Tier 1: Screening assay ADA results (positive/negative)

Tiers 2 and 3 Humira and M923 will be used to confirm the positive status of samples scored potentially positive by the screening assay:

Tier 2: Confirmatory EU Humira assay (positive/negative); if negative this will be followed by

Tier 3: Confirmatory M923 assay (positive/negative)

Positive confirmatory assay results will be summarized by Tier (2 and 3) and overall positive (in either tier).

The number and percent of subjects testing positive for ADA or neutralizing antibodies before the dose of M923 or EU RPP and at scheduled postdose assessments will be presented by treatment arm. The time to seroconversion will be summarized by treatment arm using mean, median, standard deviation and range where appropriate.

The number and percentage of subjects who had at least one ADA-positive result will be provided by treatment arm. Similar analysis may be performed for subjects with predose

ADA-negative results and with at least one, two or three postdose ADA-positive result as appropriate. Similar analysis may also be performed for subjects with ADA titers within certain ranges (to be determined).

The immunogenicity following the transition from EU RPP to M923 as compared with continuous use of EU RPP will be evaluated with the number and percentage of subjects who had at least one ADA-positive by treatment arm and by treatment period (similar to those defined in the study protocol section 13.4.4.2). Analyses of immunogenicity will be performed both for ADA and nADA for AEs before and after ADA positive at any time. Overall AEs by ADA positive at any time or negative at all visits and Hypersensitivity reactions, including those identified via MedDRA SMQ vs ADA positive at any time. This will then be repeated for injection site reactions.

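### SAP 10 relates adverse events to antibody status without time at risk, so its tables can create or hide an association, in either direction

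*SAP*

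**What the plan says.** SAP 10 sets out two ways of relating antibody status to safety. The first is a before/after split: "Analyses of immunogenicity will be performed both for ADA and nADA for AEs before and after ADA positive at any time". The second classifies each subject once for the whole study, by whether any sample was ever positive: "Overall AEs by ADA positive at any time or negative at all visits and Hypersensitivity reactions, including those identified via MedDRA SMQ vs ADA positive". Local reactions get the same layout: "This will then be repeated for injection site reactions". SAP 10 states no denominator, exposure adjustment, time-at-risk rule or landmark for any of these.

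SAP 8.1 does not fill the gap. Its AE tables use subject percentages and event counts: "The number and percentage of subjects with an AE, as well as the total number of AEs, will be summarized for each treatment arm and" by period. Person-time appears only under extent of exposure in SAP 6.5 ("Exposure will also be calculated and summarized in terms of patient treatment years") and is not linked to AEs or ADA status. Protocol 13.4.4.2 and 13.4.4.3 add no person-time method.

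On-treatment sampling is fixed by Protocol 10.3.2: "PK and immunogenicity (Weeks 8, 16, 17, 21, 25, 29, 37, and 41"). Baseline, Week 48/end of treatment and Week 52 are added elsewhere in the protocol. The first scheduled post-dose result is therefore at Week 8. SAP 8 says of the safety data that "No formal hypothesis testing of safety data is planned".

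**The concern.** A subject first positive at Week 8 has 8 weeks in which to have an event before positivity and 40 weeks after it, up to Week 48. A subject first positive at Week 37 has 37 and 11. Counts or percentages compared across such windows mainly reflect when the antibody was detected.

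In the ever/never comparison, status is fixed by results obtained after baseline. Events that precede the antibody are credited to the positive group. Subjects who leave early have had less chance to turn positive and bring shorter follow-up to the negative group.

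These are the only tables in the documents that link antibody status to AEs. Immunogenicity and the safety of the transition are secondary objectives (SAP 1.1.2), and safety and immunogenicity results to Week 25 go to regulators in an interim report (SAP 5.1). If seroconversion timing differed between products, the before/after tables would differ between them even with identical AE rates.

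**Working it through.** The plan gives no figure for this analysis, so there is none to reproduce. The check asks what the tables show when ADA has no effect on AEs.

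**Before/after, constant AE rate.** With first positive at week s and follow-up to week T, the expected after/before count ratio is (T − s)/s. Sampling weeks are from Protocol 10.3.2. T is 48 (end of treatment) or 25 (interim).

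| First positive (week) | T = 48 | T = 25 |
|---|---|---|
| 8 | 40/8 = 5.0 | 17/8 = 2.1 |
| 16 | 32/16 = 2.0 | 9/16 = 0.56 |
| 17 | 31/17 = 1.8 | 8/17 = 0.47 |
| 21 | 27/21 = 1.3 | 4/21 = 0.19 |
| 25 | 23/25 = 0.92 | 0 |
| 29 | 19/29 = 0.66 | – |
| 37 | 11/37 = 0.30 | – |
| 41 | 7/41 = 0.17 | – |

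Four of these eight sampling weeks give a ratio below 1 at Week 48, as do four of the five at the interim. No AE or ADA incidence is assumed.

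**Injection site reactions.** Dosing is at Weeks 0 and 1, then every odd week to Week 47: 25 dosing days. Dosing days before and after the sample are 5 and 20 for Week 8 (ratio 4.0), 9 and 16 for Week 16 (1.8), 13 and 12 for Week 25 (0.92), and 19 and 6 for Week 37 (0.32).

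**Simulated null.** The documents give no AE rate, ADA incidence or dropout after Week 16, so these are assumptions. The simulation used 2,000,000 subjects per scenario, the protocol's sampling weeks, follow-up to Week 52, a final sample for every early leaver, and AEs independent of ADA. The 5% loss to Week 16 is the planned one: (516 − 490)/516 = 5.04%.

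Percentage of subjects with an AE, ever versus never positive:

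| AE rate/week | Positive by Week 8, then hazard/week | Lost by 16 / stopped at 25 / lost later | Ever | Never | Difference (points) |
|---|---|---|---|---|---|
| 0.02 | 50%, 0.01 | none | 64.7 | 64.7 | 0 |
| 0.02 | 50%, 0.01 | 5% / 0 / 0 | 63.3 | 59.9 | +3.4 |
| 0.02 | 50%, 0.01 | 5% / 5% / 10% | 60.8 | 56.7 | +4.1 |
| 0.02 | 25%, 0.02 | 5% / 10% / 15% | 60.4 | 52.8 | +7.6 |
| 0.02 | 2%, 0.015 | 5% / 10% / 15% | 61.8 | 54.4 | +7.4 |
| 0.003 | 50%, 0.01 | 5% / 5% / 10% | 13.4 | 12.4 | +1.0 |
| 0.003 | 2%, 0.015 | 5% / 10% / 15% | 13.6 | 11.7 | +1.9 |

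In the same runs at 0.02 per week, positive subjects with an AE before versus after positivity were 21.9% versus 47.7% with early ADA (third row) and 41.5% versus 31.4% with late ADA (fifth row).

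**Sign reversal.** Both documents discontinue subjects without a PASI50 response at Week 25. Suppose this stops a fraction p of one group, with no other loss. At 0.02 per week the AE incidence is p(1 − e^−0.5) + (1 − p)(1 − e^−1.04) = 0.393p + 0.647(1 − p). With p = 10% in positives and 3% in negatives, this gives 62.1% versus 63.9%. With 20% and 5%, it gives 59.6% versus 63.4%.

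**Does person-time repair it?** With a constant AE rate, yes: the after/before and ever/never rate ratios were 1.00 in every null scenario. With AEs four times as frequent in Weeks 0–8, no. For a Week 8 converter, the before rate is 4 units and the after rate 1, a ratio of 0.25. For a Week 16 converter, the before rate is (4×8 + 8)/16 = 2.5, a ratio of 0.40. Across all converters the simulated ratio was 0.36 (early ADA) to 0.54 (late ADA), which looks protective although ADA has no effect.

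**The case against.** The strongest reply is that the tables are descriptive and no after/before ratio is a planned statistic. The immunogenicity and transition objectives are served by comparisons between arms and by treatment period, which this point does not touch. That stands, and it limits the importance. It does not make the tables interpretable, because a descriptive contrast whose sign depends on sampling dates and dropout still invites a wrong reading.

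A second reply is that early leavers are not lost to ADA testing. Protocol 10.6 seeks a termination visit and offers a follow-up visit 5 weeks after last dose, and both include immunogenicity sampling. This helps, but the simulation already gives every leaver a final sample and the shift remains.

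A third reply is that the before/after table separates out the pre-antibody events that the ever/never table mixes in. It does so only by comparing windows of unequal length.

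A reader might infer more: that seroconversion will necessarily look associated with more AEs. The documents do not support that. Late conversion, the short interim window, early clustering of AEs or unequal Week 25 discontinuation can each push a comparison the other way, and complete follow-up removes the ever/never shift in overall AE incidence.

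**Conclusion.** The concern holds in two-directional form: following SAP 10 as written gives ADA–AE tables confounded by unequal time at risk. The before/after ratios, from 5.0 down to 0.17 at Week 48, rest only on the sampling schedule, a constant AE rate and no ADA effect. The ever/never shift was +1 to +8 points in the simulated scenarios with dropout and about −2 to −4 points under the assumed unequal Week 25 discontinuation. Those sizes depend on AE, ADA and dropout rates that the documents do not give. The sponsor should correct this, but it is a matter of secondary, descriptive tables.

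**What to change.** In SAP 10:

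- Treat ADA status, and separately nADA status, as time-varying from the first confirmed positive sample. Negative time is that of never-positive subjects plus the pre-positive time of converters.
- Report AEs and hypersensitivity per patient-year and injection site reactions per injection, in negative and positive time, by arm.
- Do this within the SAP 8.1 treatment periods, or use a landmark, for example status at Week 16 and events thereafter. Period 1 spans Weeks 0 to 16 and scheduled detection starts at Week 8, so split it at Week 8 if periods are used.
- Restrict the never-positive group to subjects with at least one post-dose ADA result.
- State how subjects positive before the first dose are classified. SAP 10 considers baseline status only as an optional analysis of ADA incidence.
- Keep the planned counts as labelled descriptive tables.

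The cost is SAP wording and table programming, using dates and exposure already collected. The tables become more complex. Onset is known only to the sampling interval, so reactions before the Week 8 sample still count as ADA-negative time. A landmark also leaves earlier events out of the comparison.

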11. EVALUATION OF QUALITY OF LIFE

Descriptive statistics will be used to summarize the health-related quality of life by treatment group (Arm A and Arms B1 and B2) for observed values and change from baseline of DLQI and EQ-5D-5L scores and sub-scores by scheduled study visit for each treatment arm and analysis period (Arm A and B up to Week 16; Arm A, B1, B2, and B after Week 16).

11.1 Evaluation of DLQI

The DLQI score is calculated by summing the individual scores of each question at a given time point, resulting in a maximum of 30 and a minimum of 0. The higher the score, the more quality of life is impaired. For the analysis of responses, the subject's results are assessed on a scoring scale in which 3= Very much or Yes (applicable to question 7 only), 2= A lot, 1= A little, 0= Not at all or Not relevant. Interpretation of DLQI Scoring can be taken as 0 – 1= no effect at all on subject's life, 2 – 5 small effect on subject's life, 6 – 10 moderate effect on subject's life, 11 – 20 very large effect on subject's life and 21 – 30 extremely large effect on subject's life.

11.2 Evaluation of EQ-5D-5L

The euroqol-5 dimensions, five level (EQ-5D-5L) index comprises 5 dimensions of health (mobility, self-care, usual activities, pain/discomfort and anxiety/depression). For each dimension, respondents select which statement best describes their health on that day from a possible 5 options of increasing levels of severity (no problems, slight problems, moderate problems, severe problems and unable to/ extreme problems).

Responses for each dimension are coded as **Mobility**: 1= I have no problems in walking about; 2=I have slight problems in walking about; 3=I have moderate problems in walking about; 4= I have severe problems in walking about; 5= I am unable to walk about. **Self-Care**: 1= I have no problems washing or dressing myself; 2= I have slight

problems washing or dressing myself; 3= I have moderate problems washing or dressing myself; 4= I have severe problems washing or dressing myself; 5= I am unable to wash or dress myself. **Usual Activities:** 1= I have no problems doing my usual activities; 2= I have slight problems doing my usual activities; 3= I have moderate problems doing my usual activities; 4= I have severe problems doing my usual activities; 5= I am unable to do my usual activities. **Pain/Discomfort:** 1= I have no pain or discomfort; 2= I have slight pain or discomfort; 3= I have moderate pain or discomfort; 4= I have severe pain or discomfort; 5= I have extreme pain or discomfort. **Anxiety/Depression:** 1= I am not anxious or depressed; 2= I am slightly anxious or depressed; 3= I am moderately anxious or depressed; 4= I am severely anxious or depressed; 5= I am extremely anxious or depressed.

It should be noted that the numerals 1-5 have no arithmetic properties and should not be used as a cardinal score.

In addition to the descriptive system, respondents also assess their health today on a visual analogue scale, ranging from 0 (worst imaginable health) to 100 (best imaginable health). This score will be summarized separately using descriptive statistics for baseline, each study evaluation, and change from baseline to each evaluation.

12. EVALUATION OF EXPLORATORY OUTCOME MEASURES

CCI

13. ANALYSIS SOFTWARE

All data processing, summarization, and analyses will utilize SAS® software package, Version 9.2. If the use of other software is warranted the final statistical report will detail what software was used.

15. SUPPLEMENTS

15.1 Study 911401 Schematic

Figure 1
Study Design for Baxalta Clinical Study 911401

*Injections administered subcutaneously at Weeks 0 and 1, and then every 2 weeks in each arm. Last dose at Week 47.

Subjects in Arm B are randomized again 1:1 at Week 16 into Arms B1 and B2.

D = Day; EU RPP = Reference Protein Product; N = number of subjects; PASI = Psoriasis Area and Severity Index.

15.2 Schedule of Study Procedures and Assessments

Table 3
Schedule of Study Procedures and Assessments

Phase	Screening	Double-Blind Period																			Safety Follow-up ^s
		-4 to 0	0	1	4	8	12	16	17	19	21	25	27	29	33	37	39	41	45	48/ETV	
Week	-4 to 0	0	1	4	8	12	16	17	19	21	25	27	29	33	37	39	41	45	48/ETV	52	
Study Day	-28 to -1	1	8	29	57	85	113	120	134	148	176	190	204	232	260	274	288	316	337	365	
Visit ^r	1	2	3	4	5	6	7	8	9	10	11	12	13	14	15	16	17	18	19	20	
Informed consent	X																				
Medical history and prior medications (including prior therapy, psoriasis, and surgeries)	X																				
Inclusion/exclusion criteria	X	X ^a																			
Concomitant therapy ^b			↔																		
Randomization		X						X ^c													
Tuberculosis screening	X ^d																				
sPGA, PASI, BSA ^e	X	X	X	X	X	X	X	X	X	X	X	X	X	X	X	X	X	X	X	X	
DLQI and EQ-5D-5L ^f		X					X				X				X					X	
HIV, Hepatitis B and C viral testing	X																				
Adverse event monitoring			↔																		
Physical exam	X ^g	X		X	X		X ^g	X	X		X	X			X	X			X ^g	X	
12-lead ECG ^h	X	X					X			X			X			X				X	
Vital signs ⁱ	X	X	X	X	X	X	X	X	X	X	X	X	X	X	X	X	X	X	X	X	
PK and immunogenicity ^j		X			X		X	X		X	X		X		X		X		X	X	
Hematology, chemistry ^k	X	X	X	X	X		X	X	X	X	X		X		X		X		X	X	
Urinalysis	X	X		X	X		X	X	X	X	X				X				X	X	

Table 3
Schedule of Study Procedures and Assessments

Phase	Screening	Double-Blind Period																			Safety Follow-up ^s
		0	1	4	8	12	16	17	19	21	25	27	29	33	37	39	41	45	48/ETV		
Week	-4 to 0	0	1	4	8	12	16	17	19	21	25	27	29	33	37	39	41	45	48/ETV	52	
Study Day	-28 to -1	1	8	29	57	85	113	120	134	148	176	190	204	232	260	274	288	316	337	365	
Visit ^r	1	2	3	4	5	6	7	8	9	10	11	12	13	14	15	16	17	18	19	20	
Pregnancy test ^l	X	X		X	X	X	X	X		X	X		X	X	X		X		X	X	
Injection training ^m		X																			
Study drug injection onsite ⁿ		X	X						X	X	X	X				X	X				
Post-injection monitoring onsite ^o		X	X						X	X	X	X					X	X			
Injection site evaluation ^p		X	X						X	X	X	X	X	X	X	X	X	X	X	X	
Study drug dispensing			X	X	X	X	X	X	X	X	X	X	X	X	X	X	X	X	X		
Study drug return																				X	
Study diary dispensing/collection ^q		X										X								X	

AE = adverse event; BSA = body surface area; DLQI = Dermatology Life Quality Index; ECG = electrocardiogram; ETV = end of treatment visit;

HIV = human immunodeficiency virus; EQ-5D-5L = EuroQoL-5 dimensions- 5 levels; PA: posterior-anterior, PASI = Psoriasis Area and Severity Index; PK = pharmacokinetics; PPD = purified protein derivative; sPGA = static Physician Global Assessment; TB = tuberculosis

^a Inclusion/exclusion criteria to be reviewed before randomization. The screening visit needs to occur with enough time prior to randomization to ensure eligibility requirements for the screening visit are met.

^b Concomitant therapy will include pharmacologic and nonpharmacologic therapies.

^c Subjects in Arm B are randomized again at this visit.

^d Subjects will receive testing if not received within previous 3 months and/or doesn't have documented history of prior positive TB test result or active TB infection. Testing includes QuantiFERON, T-SPOT, or PPD and a radiograph or comparable imaging with negative finding for TB or other similar infections (PA or PA and lateral view).

^e sPGA, PASI and BSA assessments should be conducted at screening and at baseline before randomization and study drug administration to ensure eligibility.

^f All subject-completed assessments (ie, patient-reported outcomes) should be completed before any other assessments are done.

Table 3
Schedule of Study Procedures and Assessments

Phase	Screening	Double-Blind Period																		Safety Follow-up ^s
		0	1	4	8	12	16	17	19	21	25	27	29	33	37	39	41	45	48/ETV	
Week	-4 to 0	0	1	4	8	12	16	17	19	21	25	27	29	33	37	39	41	45	48/ETV	52
Study Day	-28 to -1	1	8	29	57	85	113	120	134	148	176	190	204	232	260	274	288	316	337	365
Visit ^r	1	2	3	4	5	6	7	8	9	10	11	12	13	14	15	16	17	18	19	20

^g Complete physical exam will be conducted at screening, Week 16, and 48. All other physical exams will be brief and should include heart, lungs, abdomen and extremities and skin, and any other assessments required to evaluate AEs.

^h ECG should be recorded before blood sampling.

ⁱ Vital signs should be taken before blood sampling. Height will be measured at Visit 1 only.

^j PK and immunogenicity blood samples are to be collected in all subjects at these time points. Samples should be obtained prior to administering study drug if an administration occurs at that visit and before any hematology/chemistry samples to be drawn at that visit.

^k Blood samples will be taken before injection of study drug, after ECG and vital signs assessments, and after PK and immunogenicity sampling if applicable.

^l Pregnancy testing is only required for female subjects of childbearing potential. Serum test will be done at screening; all other assessments are done on urine.

^m Self-injection training should be provided with the first injection, with subject or caregiver performing the second injection at the first visit. Additional training can be provided with the Week 1 injection, if needed. At all other visits where the injection occurs in clinic, the subject or caregiver should administer the injection and be observed to ensure correct administration.

ⁿ Study drug will be administered in clinic after all required assessments and blood sample collections have been completed at Weeks 0, 1, 17, 19, 21, 25, 27, 37, and 39. Injections will occur at home in-between clinic visits on Weeks 3, 5, 7, 9, 11, 13, 15, 23, 31, 35, 43 and 47. At Weeks 29, 33, 41, and 45, the study drug injections will be completed at home after the assessments are completed at the clinic.

^o When injection occurs in the clinic, subjects should be observed for a minimum of 2 hours in the clinic after injection at Weeks 0, 1, 17, 25, and 37. Subjects should be observed for 30 minutes after injection at Weeks 19, 21, 27, and 39. At Week 48, only return of study drug will occur.

^p The investigator or a qualified designee will evaluate the current injection sites 30 minutes (\pm 10 minutes) after study drug administration in the clinic at Weeks 0, 1, 17, 19, 21, 25, 27, 37, and 39. They should also evaluate any immediately prior injection site at each subsequent visit as applicable. For injections given at home, injection site reactions will be recorded in the subject diary. There will be no injection at Week 48 (Visit 19), but injection site evaluation for previous injections will occur.

^q The subject should bring the diary at all visits between Weeks 1 and 48. The investigator will review the diary for completeness, request missing information periodically and in a timely manner, photocopy and store the applicable pages in the source documents until the original diary is collected. At Week 25, the subject diary will be collected by the investigator and a new one will be provided until Week 48.

^r Visit windows are \pm 1 day at Visit 3, \pm 3 days for Visits 4-19 and \pm 2 weeks for Visit 20. Reference for visit windows/study day is scheduling based

Table 3
Schedule of Study Procedures and Assessments

Phase	Screening	Double-Blind Period																			Safety Follow-up ^s
		0	1	4	8	12	16	17	19	21	25	27	29	33	37	39	41	45	48/ETV		
Week	-4 to 0	0	1	4	8	12	16	17	19	21	25	27	29	33	37	39	41	45	48/ETV	52	
Study Day	-28 to -1	1	8	29	57	85	113	120	134	148	176	190	204	232	260	274	288	316	337	365	
Visit ^r	1	2	3	4	5	6	7	8	9	10	11	12	13	14	15	16	17	18	19	20	

on Visit 2/Baseline Visit.

^s If the subject does not show up to the clinical visit, the site should try to contact the subject by phone for at least 8 weeks after the scheduled follow-up visit and obtain information regarding the occurrence of adverse events, psoriatic and concomitant treatments and pregnancy status. Discontinuing subjects will be invited to perform this visit 5 weeks after last IP dose.

